8.7.3 ANALYSIS OF OTHER SECONDARY EFFICACY ENDPOINTS

Cumulative radiation dose to development of severe oral mucositis: Total cumulative dose of radiation (in Gy units) until the date of first severe OM (WHO grade 3 or 4) will be calculated for each subject and summarized by treatment group using descriptive statistics in the mITT population. Similarly, the cumulative radiation dose up to the first observed ulcerative oral mucositis (WHO grades 2-4) will be tabulated. If a subject does not experience severe OM during the study, the full cumulative radiation dose will be used. The difference between treatment groups will be evaluated using the stratified CMH test (with modified ridit scores). This test will determine whether the AG013 group achieved a higher cumulative radiation dose before onset of severe OM, compared to the placebo group.

Patient-reported pain: The average of patient-reported MTS scores, graded on a scale from 0 (no soreness) to 4 (extreme soreness), will be summarized by treatment group during each study week as well as for the last 7 days of treatment in the mITT population.

The difference between treatment groups will be evaluated using the stratified CMH test (with modified ridit scores) to determine whether or not AG013 reduces pain.

Other Diary Outcomes: For other diary items: overall health, limited in swallowing, drinking, eating, talking and sleeping, overall soreness and diarrhea descriptive statistics will be produced for each treatment and by study week as well as for the last 7 days of treatment in the mITT population. However, no significance tests will be performed.

Analgesic use: Use of analgesics (parenteral, oral, or transdermal) to control oral pain will be examined by displaying number and percentages of subjects in the mITT population taking:

- Topicals such as viscous lidocaine
- OTC analgesics such as acetaminophen or ibuprofen
- PO opioids such as Vicodin or Percocet
- Parenteral opioids such as morphine or Fentanyl

Also, PO and Parenteral opioids will be combined to form a category for all opioids. Pvalues for all opioids and parenteral opioids will computed using the stratified CMH test (with modified ridit scores).

All the patient-level secondary endpoints will be listed together with the primary endpoint. Listings of radiation therapy data, OMDQ, and analgesics will be created as well.

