1.1.2 Clinical Effects of Oral Mucositis

The severity of OM varies from superficial erythema, accompanied by soreness, to full-thickness mucosal ulcerations, necessitating parenteral narcotics for pain control (Scully et al., 2006). Among patients receiving myeloablative CT regimens or RT to the head and neck, OM is the most commonly cited bothersome adverse event (AE) associated with treatment (Rose-Ped et al., 2002).

The clinical impact of OM is profound, especially when ulceration is present. Even OM described as slight to moderate is associated with increased oral pain, weight loss, the need to modify diet, dehydration, and reduced performance status (Elting et al., 2007). Oral mucositis results in loss of critical functions, such as the ability to eat and to swallow, which can lead to dehydration, weight loss, and the need for nutritional support (e.g., gastrostomy tube placement). Furthermore, the ulcerations associated with OM are a frequent site of secondary infections and, in myelosuppressed patients, may act as portals for systemic bacterial spread (Reuscher et al., 1998). Treatment breaks prompted by patients' inability to tolerate the symptoms associated with OM compromise cancer therapy. And there is a strong association between OM and diminished quality-of-life (QOL) outcomes (Elting et al., 2008).

Besides its symptomatic toll, OM is associated with a number of negative health and economic outcomes, including increased analgesic and antibiotic use, number of febrile days, need for parenteral nutrition, prolonged length of hospital stay, and

This document contains confidential information. It is intended solely for the use of the principal investigator, co-investigators, staff, appropriate institutional review boards or ethical committees, and other required regulatory bodies.

increased resource use and associated cost. In granulocytic patients, mucositis is strongly associated with an increased risk of bacteremia and sepsis (Reuscher et al., 1998). Among patients treated for HNC, even mild OM results in more frequent hospitalization and breaks in treatment (Vera-Llonch et al., 2006).

Despite its frequency and significance, there is no approved intervention for RT-induced OM in HNC. Furthermore, currently there is a single agent approved as a treatment for OM, Kepivance[®], and its application is limited to OM associated with conditioning regimens prior to stem cell transplant for the treatment of hematologic malignancies.

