This document contains confidential information. It is intended solely for the use of the principal investigator, co-investigators, staff, appropriate institutional review boards or ethical committees, and other required regulatory bodies.

be used to compare proportions and test whether or not AG013 reduces the incidence of severe OM.

Duration of ulcerative OM: The duration of ulcerative OM (WHO grade 2, 3 or 4) will be calculated in a manner similar to duration of severe OM. That is, the duration of ulcerative OM will be calculated as the number of days from the onset of ulcerative OM (first time a WHO grade 2, 3 or 4 is observed) to the day when ulcerative OM has resolved (first time WHO grade 0 or 1 is observed after last WHO grade 2, 3 or 4). A similar imputation scheme will be used in the event that subjects die or withdraw prior to resolution of OM to grade 0 or 1. The stratified CMH test (with modified ridit scores) will be used to compare treatment groups and test whether or not AG013 reduces the duration of ulcerative OM.

Time to onset of ulcerative OM: Time to onset of ulcerative OM (WHO grade 2, 3 or 4) will be calculated and analyzed as described above for severe OM.

Incidence of ulcerative OM: Incidence of ulcerative OM (WHO grade 2, 3 or 4) will be calculated and analyzed as described above for severe OM.

Cumulative radiation dose to development of severe oral mucositis: Total cumulative dose of radiation (in Gy units) until the date of first severe OM (WHO grade 3 or 4) will be calculated for each subject and summarized by treatment group using descriptive statistics. Similarly, the cumulative radiation dose up to the first observed ulcerative oral mucositis (WHO grades 2-4) will be tabulated. The difference between treatment groups will be evaluated using the stratified CMH test, with modified ridit scores. This test will determine whether the AG013 group achieved a higher cumulative radiation dose before onset of severe OM, compared to the placebo group.

Patient-reported pain: The average of patient-reported mouth and throat soreness (MTS) scores, graded on a scale from 0 (no soreness) to 4 (extreme soreness), will be summarized by treatment group during each study week. The difference between treatment groups will be evaluated using the stratified CMH test, with modified ridit scores, to determine whether or not AG013 reduces pain.

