5.5 PHARMACOKINETIC (PK) AND PHARMACODYNAMIC (PD) ENDPOINTS

- Assessment of biomarkers (primarily pro- and anti-inflammatory cytokines)

PK profile of AG013 based on blood/serum samples and buccal smears in a subset of subjects (15 subjects on AG013 and 15 subjects on placebo, in up to 10 sites).

Note: the PD endpoints are considered to be optional endpoints to be evaluated only in case of positive outcome of the study.

- 5.6 EXPLORATORY EFFICACY ENDPOINTS FOR OM (LINKED TO PRIMARY ENDPOINT)
- Incidence of severe mucositis (WHO grades 3 or 4) within subgroups defined by cumulative radiation doses of 30 Gy, 40 Gy, 50 Gy, 60 Gy, and 70 Gy
- The area under curve (AUC) of an OM severity-time curve

- Mucositis severity parameters (incidence, duration, time to onset of grades 3, 4 and 2, 3, 4) based on National Cancer Institute-Common Terminology Criteria for Adverse Events (NCI-CTCAE) v4.0 and Radiation Therapy oncology Group (RTOG) criteria

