8.7 EFFICACY ENDPOINTS AND ANALYSIS

8.7.1 ANALYSIS OF PRIMARY EFFICACY ENDPOINT

The duration of severe OM (WHO grade 3 or 4) will be calculated as the number of days from the onset of severe OM (first time a WHO grade 3 or 4 is observed) to the day when severe OM has resolved (first time WHO grade 2 or less is observed after last WHO grade 3 or 4). This calculation allows for fluctuation in severity grades and considers separate episodes of SOM to be additive. Durations of 0 will be assigned to subjects who do not experience severe OM, even if the subject was not followed for the full planned period. Any subject who dies or withdraws prior to resolution of severe OM (i.e., with grade 3 or 4 at last assessment) will be assumed to have severe OM for the remainder of the observation period. In these cases, duration will be calculated as the number of days from the first onset of severe OM (WHO grade 3 or 4) until the end of Short Term Follow-up phase which will be taken as Week 13 (Day 91 relative to start of CRT). All available OM assessments will be used to derive efficacy endpoints, including WHO grades recorded during the treatment phase and the short-term follow-up period.

The intent of the primary statistical analysis is to test the superiority of AG013 over placebo in reducing the duration of severe OM. The null hypothesis is that the AG013 and placebo groups have the same duration (in days) of severe OM. The alternative hypothesis is that the duration of severe OM in the two treatment groups is different.

The generalized CMH method, stratified by cisplatin regimen (weekly versus tri-weekly), by HPV status (positive versus negative) and region (US versus Europe), will be used for the primary efficacy analysis. In case of erroneous stratification at baseline, the corrected stratification data will be used for the analysis. Standardized mid-ranks (also known as modified ridit scores) will be used for the test statistic. This generalized CMH test follows a chi-square distribution with 1 degree of freedom. The efficacy analysis will be performed in the ITT, mITT, and PP populations, with the ITT designated as primary. Below is the sample code that performs this analysis:

```
proc freq
```

```
data=test;
tables STRATUM*TRTPN*OM_DURATION / CMH SCORE=MODRIDIT;
run;
```

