8.7.2 ANALYSIS OF KEY SECONDARY EFFICACY ENDPOINTS

Statistical methods for the calculation and analysis of secondary efficacy endpoints are provided below. For each endpoint, significance testing will evaluate the superiority of AG013 compared to placebo; two-sided tests will be used to reject the null hypothesis (no difference between groups) in favor of the alternative hypothesis (there is a difference between groups). The analysis of all key secondary efficacy endpoints will be performed for the ITT, mITT and PP populations.

Note: The OM assessment period includes all OM Assessments performed, including the short-term follow-up period.

To control the experiment-wise Type 1 error rate at 5%, significance tests of the key secondary efficacy endpoints will be performed in the hierarchical order listed below. As specified in the protocol, the mITT population will be the main analysis and guide the hierarchical order of testing. To support these results, the same analyses will be repeated for ITT and PP populations. Each analysis will control for stratifications factors. All the analyses described below will be performed for the purpose of displaying summary statistics, but once the first in the sequence of tests yields a p-value that exceeds 0.05, the nominal p-value for this and subsequent endpoints in the series will be declared non-significant.

Time to onset of severe OM: Time to onset of severe OM (WHO grade 3 or 4) will be calculated as the elapsed time (in days) from the start of CRT until the date of first OM assessment grade 3 or 4. Subjects who do not experience an event by the end of the OM assessment period will be censored on the date of last OM assessment. Subjects with no post-baseline OM assessments will be censored on Day 1. Kaplan-Meier estimation methods and the stratified log-rank test will be used to compare time-to-event distributions and test whether or not AG013 delays the onset of severe OM. The log-rank test will be stratified by cisplatin regimen, HPV status and region. Below is the sample SAS code that performs the intended analysis:

```
proc lifetest
```

```
data=test;
time Time_to_Onset*censor(1);
strata CIS_GRP HPV REGION / group=TRTPN;
run;
```

Incidence of severe OM: The incidence of severe OM (WHO grade 3 or 4) will be calculated as the number of subjects with at least one OM WHO grade 3 or 4, divided by

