8.7.4 EXPLORATORY EFFICACY ENDPOINTS

Exploratory efficacy analyses will be conducted for the mITT population only. The effects of AG013 will be explored on the basis of the following:

Descriptive statistics will be presented for the incidence of severe OM (WHO grades 3 or 4) within subgroups receiving each of the following cumulative radiation doses: <=30 Gy, >30 and <= 40 Gy, >40 and <= 50 Gy, >50 and <= 60 Gy, and > 70 Gy. As with the secondary endpoint analysis, incidence will be defined as the proportion of subjects in each subgroup having at least one grade 3 or 4 OM assessment.

The distribution of OM severity grades at each visit will be provided for CTC and RTOG rating scales. These summary tables will display the number and percentage of patients per OM grade at each visit, by treatment group, for the mITT population.

For each subject, oral mucositis severity scores (WHO grades 0-4) at each time point will be used to calculate AUC using the trapezoidal rule. Average severity-by-time curves will

be generated and plotted for each treatment group, and compared using the Wilcoxon rank-sum test. Descriptive statistics for AUC values will be presented.

Incidence, duration and time to onset of grades 3 and 4 and grades 2, 3, and 4 OM as per NCI CTCAE and RTOG criteria will be analyzed separately, using the same methodology as described for the primary and secondary endpoints. Listings of NCI CTCAE and RTOG grades will be prepared, as well as listings of the calculated endpoints.

Frequency and duration of RT interruptions: The number of subjects in each treatment group with an unplanned break in RT during the 7- to 9-week regimen will be tabulated. Subjects with an interval of 5 days or more without an administration of RT, or who discontinue RT prior to completing the planned RT regimen, will be considered to have an unplanned break in RT. The duration of unplanned RT interruptions (in days) will also be summarized by treatment group using descriptive statistics. For subjects who prematurely discontinue RT, the time from the last dose of RT to the prescribed end date of the regimen will be used in the calculation.

All the RT data will be listed. Calculated values for the above listed endpoints will be listed separately.

The number of unplanned office visits, ER visits, hospitalizations, and non-prophylactic gastrostomy tube placements (US sites only) in each treatment group will be tabulated.

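### Dose to onset of severe OM counts a total dose as an onset dose for subjects who never had it; separately, the exploratory dose table has no row for totals above 60 and up to 70 Gy

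*SAP*

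**What the plan says.** **Dose to onset.** Protocol 10.5 defines the endpoint as the cumulative Gy up to the first severe OM. It specifies the test ("The difference between treatment groups will be evaluated using the stratified CMH test, with modified ridit scores") but gives no rule for subjects who never have severe OM. SAP 8.7.3 adds one: "If a subject does not experience severe OM during the study, the full cumulative radiation dose will be used". It keeps the ridit test and says the test will show whether AG013 subjects reached a higher dose before onset. The rule names severe OM only; nothing is said for subjects without ulcerative OM. SAP section 9 does not list the addition.

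**The parallel endpoint.** For time in days to the same event, SAP 8.7.2 says: "Subjects who do not experience an event by the end of the OM assessment period will be censored". It uses Kaplan-Meier and a log-rank test stratified by cisplatin regimen, HPV status and region. It also notes: "The OM assessment period includes all OM Assessments performed, including the short-term follow-up period".

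**Dose bands.** SAP 5.6 lists "cumulative radiation doses of 30 Gy, 40 Gy, 50 Gy, 60 Gy, and 70 Gy" as the subgroups for the exploratory incidence table. SAP 8.7.4 gives the bands as "<=30 Gy, >30 and <= 40 Gy, >40 and <= 50 Gy, >50 and <= 60 Gy, and > 70 Gy".

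**The concern.** A ridit score depends only on the size of the number entered. For a subject without severe OM, that number is the total dose, which reflects the prescribed plan and whether radiotherapy was stopped early. It is a lower bound on the onset dose, not an onset dose. The comparison therefore mixes three things: when severe OM began, what was prescribed, and who stopped early.

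This could cost power. If early stops differ between arms, it could also produce a difference unrelated to OM. The reported mean or median would not be an onset dose either.

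The band gap is simpler: programmed as written, the table silently loses subjects.

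**Working it through.** **1. The plan's own figures.** The documents give no power figure for this endpoint. The two figures in SAP section 6 concern other endpoints:
- Duration: noncentrality 5 / (10.8 × √(2/80)) = 2.93, giving 82.9% power by t-test against a stated approximate 80%.
- Incidence: 75% vs 50% with 80 per group gives 88.3% by exact Fisher enumeration against a stated approximate 85%.

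Both stated figures are a little conservative. Only the 75% and 50% incidences are used below.

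**2. How many values are not onset doses.** At those incidences, 25% × 80 = 20 placebo and 50% × 80 = 40 AG013 subjects would carry a total dose: 60 of 160, or 37.5%.

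**3. What the rule does to the ordering.** The analysed value is the smaller of dose at first severe OM and total dose received.

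| Subject A | Subject B | Result |
|---|---|---|
| Never severe, 60 Gy plan completed: 60 | Onset at 64 Gy: 64 | A ranks worse than B |
| Stops RT at 20 Gy, never severe: 20 | Onset at 20 Gy: 20 | Tie |
| First severe after the last fraction, total 70 Gy: 70 | Never severe, total 70 Gy: 70 | Tie |

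Row 1 needs no early stopping, because eligible plans run from 50 to 72 Gy. In row 2, the primary analysis gives subject A the best possible score: "Durations of 0 will be assigned to subjects who do not experience severe OM, even if the subject was not followed". Row 3 arises because OM is assessed beyond the end of radiotherapy.

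**4. Size, by simulation.** 2,000 trials per scenario, 100 per arm, eight strata of unequal size. Assumed inputs, none of which is in the documents except the 75%/50% incidences:
- constant hazard per Gy from 16 Gy, reaching incidence p by 70 Gy: hazard = −ln(1 − p)/54, that is 0.0257 (75%), 0.0128 (50%) and 0.0194 (65%, used in both arms for no effect);
- onset seen at the next 5 Gy step;
- planned dose 60, 66 or 70 Gy with weights 0.35, 0.15 and 0.50;
- early leavers stop uniformly between 2 and 56 Gy.

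The comparison is the planned ridit test against a stratified log-rank test on Gy that censors non-events at their last dose. Simulation standard error is √(0.05 × 0.95/2000) = 0.5 points at 5%, and 0.7 points at 90%.

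| Power, 75% vs 50% | Ridit | Log-rank |
|---|---|---|
| No leavers | 92% | 96% |
| 10% leavers per arm | 83% | 94% |
| 20% leavers per arm | 69% | 91% |
| No leavers, about 11–12% first severe after RT | 84% | 96% |
| 20% leavers per arm, about 11–12% first severe after RT | 59% | 91% |

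| Leavers by arm, no effect | Ridit type I error |
|---|---|
| 20% / 20% | 5% |
| 5% / 10% | 6% |
| 10% / 15% | 7% |
| 10% / 20% | 13% |
| 10% / 25% | 22% |

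Log-rank type I error was 4–5% throughout. The excess ridit rejections went almost wholly against the arm with more leavers.

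A second, unstratified simulation used 80 per arm, onset uniform over 20–60 Gy, 30% on 60 Gy and 70% on 70 Gy plans, and stops uniform over 10–40 Gy. It agreed in direction. Power was 78% vs 89% with no stops and 62% vs 85% with 10% per arm. With 75% incidence in both arms and stops of 5% vs 15%, type I error was 14% vs 5%.

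**5. Bands.** With fractions of 2.0 to 2.2 Gy (Protocol 4.2), 30 × 2.1 = 63, 30 × 2.2 = 66 and 35 × 2.0 = 70 Gy fall in no band. Totals of 25 × 2.0 = 50, 30 × 2.0 = 60 and 35 × 2.05 = 71.75 Gy do. The gap is 70 − 60 = 10 Gy of the 72 − 50 = 22 Gy eligible planned range. That is a width on the dose scale, not a share of subjects.

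**The case against.** **Estimand and overlap.** The rule is explicit, and the value can be read as dose delivered free of severe OM. On that reading, rows 1 and 2 are not errors, and the contrast with the primary endpoint compares two different quantities. Time to onset is already tested with censoring, and with single daily fractions Gy closely tracks treatment days. This stands in part. But SAP 8.7.3 describes its test as one of dose before onset, so the target must be stated either way. Row 3 is a problem if late onset is to be distinguished from none.

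**Informative stopping.** Protocol 1.1.2 says that treatment breaks prompted by patients' "inability to tolerate the symptoms associated with OM compromise cancer therapy". If subjects stop because severe OM is imminent, censoring is informative. With leavers stopping 2–10 Gy before their own onset, power was equal (92% vs 92% at 20% per arm). At 10%/25% leavers under no effect, log-rank type I error reached 12%, favouring the arm with more leavers, while ridit stayed at 5%. This stands, and is why the ridit test should be kept as a sensitivity analysis.

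**Assumed stopping doses.** If stops fall between 40 Gy and the planned total, the power gap is only about 5 to 8 points and ridit type I error at 10%/25% is about 5–7%, not 22%. This also stands: the larger figures need early and unequal stopping.

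**Ulcerative OM.** Protocol 1.1.1 says virtually all such patients develop it, so few subjects would need the missing rule. That makes this gap minor.

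**Conclusion.** Both halves hold on the text. The dose-to-onset analysis enters total doses as onset doses in a test that cannot tell them apart. The dose table omits totals above 60 and up to 70 Gy although SAP 5.6 lists 70 Gy.

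Under the assumed inputs, the loss of power is about 4 points if everyone completes radiotherapy and 11 points at 10% early leavers per arm. It disappears if leavers stop just before their own onset. With equal leavers, type I error is sound; it rises clearly only when early stops are frequent, early in the course and markedly unequal. The documents give no leaver rate, plan mix or onset distribution, so the figures show direction and rough size; the ordering faults do not depend on them.

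The reach is limited to a secondary endpoint outside the SAP's five-endpoint hierarchy and a descriptive exploratory table. It is worth correcting before database lock.

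**What to change.** **Dose to onset (SAP 8.7.3).**
- Analyse dose to first severe and to first ulcerative OM with cumulative Gy as the time axis.
- Censor non-events at their last dose. Count an onset first seen after the last fraction as an event at the total dose.
- Use Kaplan-Meier by arm and a log-rank test stratified by the three randomisation factors.
- State the non-informative-censoring assumption, and present early radiotherapy stops by arm alongside (SAP 8.7.4 already plans to tabulate them).
- Keep the planned ridit analysis as a sensitivity analysis.
- Record the change in SAP section 9, since Protocol 10.5 specifies the ridit test.

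If dose delivered free of severe OM is what is wanted, say so and give the same rule for ulcerative OM.

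**Bands (SAP 8.7.4).** Add a row for above 60 and up to 70 Gy. Optionally, also report Kaplan-Meier incidence at 30, 40, 50, 60 and 70 Gy.

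**Cost.** A paragraph in 8.7.3, an entry in section 9 and one table row. The PROC LIFETEST code in SAP 8.7.2 can be reused with Gy in place of days. No new data are needed, and SAP 8.1 allows updates before database lock.
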